7.3.3 Quality of Life as Measured by the SF-36 Score

The Short Form (36) Health Survey is a 36-item, patient-reported survey of patient health. The SF-36 is a measure of health status and the survey will be conducted according to the SF-36 quality of life questionnaire Version 2.0.

The assessments will be performed at time points indicated in the schedule of events ([Table 2](#)).

7.4 Sample Size Calculations

A minimum of 60 subjects will be enrolled in the study. Subjects will receive either 200 mg BID or 400 mg BID of SKI-O-703 or placebo in a 2:2:1 ratio.

Based on [Podolanczuk et al \(2009\)](#) at least 50% of subjects in the active treatment group will be responders (R). A sample size of 24 subjects per active treatment group and 12 subjects in the placebo group will provide approximately 82.7% power to detect a difference between response rates of 50% and 1% in the active treatment and placebo groups, respectively, at the 2-sided 5% significance level. The test statistic used in the sample size calculation was the 2-sided Fisher's Exact test using the normal approximation method.

Subjects that do not receive the study drug or do not provide at least 1 post baseline measurement will be excluded from the analysis above and replaced.

There will be no adjustment for multiple comparisons. The sample size calculation was performed using PASS 15 Power Analysis and Sample Size Software (2017). NCSS, LLC. Kaysville, Utah, USA, ncss.com/software/pass.

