3.1.2 Rationale of Study Design

This double-blind, placebo-controlled study is designed to evaluate the efficacy, safety, tolerability, PK, and PD of SKI-O-703 in persistent and chronic ITP patients. The results of this study will guide on further clinical evaluation of SKI-O-703 patients with ITP. The double-blind placebo-controlled design has been selected to minimize bias in the evaluation of the safety, efficacy, PK, and PD.

Since the 400 mg BID dose level has not been investigated in healthy volunteer studies, a safety run-in group will be implemented. To protect the study blind, 5 subjects will be included in the safety run-in period to reflect the overall 2:2:1 randomization, resulting in 2 subjects each being dosed at 400 mg and 200 mg BID and 1 subject being dosed with placebo. An interim safety and PK data review will be performed by the DMC once the subjects in the safety run-in period complete their Day 8 (± 2 days) assessments. Further

enrollment in each treatment group will only resume after safety and PK data of the first week for the first 5 subjects are reviewed and considered satisfactory by the DMC.

Serial blood samples (5 mL) for PK assessment of SKI-O-592 and its metabolites (M2 and M4) from all subjects in the PK/PD subset will be obtained from this study, which in turn would help refine the sparse sampling approaches needed for later Phase 3 studies leading to a better population PK analysis in Phase 3.

The power of a statistical test is typically a function of the magnitude of the treatment effect, the designated Type I error rate (α , risk of false-positive result) and the sample size (n). When designing a trial, it is important to decide upon the desired study power (typically 80% for a Phase 2 study) and calculate the necessary sample size to achieve this goal. Since it is often not feasible to conduct large trials during early stage of development, it is necessary to identify the strategies to optimize the statistical power of smaller studies.

In this study, platelet response, defined as platelet count $\geq 30,000/\mu\text{L}$ and doubling the baseline (average of 2 previous counts), at any visit during the treatment period and without use of rescue medication, is selected as the primary endpoint.

4 Subject Selection and Withdrawal Criteria

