7.7 Statistical Analysis Methodology

Statistical analysis will be performed using SAS software Version 9.4 or later. The results for each efficacy endpoint will be summarized by visit and treatment for all subjects within the ITT analysis set using descriptive statistical methods. Continuous variables (quantitative endpoints) will be summarized using the mean, the standard deviation (SD), median, range (minimum value and maximum value), and interquartile. Categorical variables (qualitative endpoints) will be summarized using frequency counts (number) and percentages. Data will be listed in data listings.

Details of the statistical analyses, methods, and data conventions will be described in the statistical analysis plan.

All statistical tests will be 2-sided using a 5% significance levels, leading to 95% (2-sided) confidence intervals (CIs). This will be used for each pairwise comparison with placebo, ie, there will be no adjustments for multiplicity since this is a Phase 2 study.

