7.7.3 Analysis of Platelet Response

The primary efficacy endpoint will be summarized as overall platelet response rate (ORR) by treatment group and analyzed using Fisher's exact test to compare the difference in ORR between each active treatment group and placebo. A logistic regression model will also be performed on platelet response and include treatment, baseline platelet count and prior TPO-receptor agonist use, provided there are enough subjects in each subgroup. The odds ratio for the treatment effect compared to placebo (together with 95% CI and p-value) will be provided.

Summary statistics will be provided on the number (%) of subjects achieving platelet response by each treatment group and the combined active treatment group. Fisher's exact test on the differences in the ORR will therefore be provided for:

- Each active treatment group (200 mg BID, 400 mg BID) vs. placebo
- Combine active treatment groups vs. placebo
- 200 mg BID vs. 400 mg BID.

Furthermore, summary statistics will be provided on the number (%) of subjects achieving platelet response by each treatment group and the subgroups defined in [Section 7.6](#).

A subject will be classified as a platelet responder if subject shows at least 1 platelet count $\geq 30,000/\mu\text{L}$ and doubling the baseline (average of 2 previous counts), at any visit during treatment period, without use of rescue medication. The ITT analysis set will be used in the analysis of the primary endpoint.

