#### **4.4. Sample Size**

A minimum of 60 patients will be enrolled in the study. Patients will receive either 200 mg BID or 400 mg BID of SKI-O-703 or placebo in a 2:2:1 ratio.

Based on [Podolanczuk et al \(2009\)](#) at least 50% of patients in the active treatment group will be responders (R). A sample size of 24 patients per active treatment group and 12 patients in the placebo group will provide approximately 82.74% power to detect a difference between response rates of 50% and 1% in the active treatment and placebo groups, respectively, at the 2-sided 5% significance level. The test statistic used in the sample size calculation was the 2-sided Fisher's Exact test using the normal approximation method.

Patients that do not receive the study drug or do not provide at least 1 post baseline measurement will be excluded from the analysis above and replaced.

There will be no adjustment for multiple comparisons. The sample size calculation was performed using PASS 15 Power Analysis and Sample Size Software (2017). NCSS, LLC. Kaysville, Utah, USA, [ncss.com/software/pss](http://ncss.com/software/pss).

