#### 8.1.1. Primary Analysis

The platelet responses after using rescue medication during treatment period will be set to missing and will be imputed as the average of the last 2 previous non-missing platelet counts. For example, if platelet count in Week 2 Day 8, Week 3 and Week 5 are 45,000, missing, and 48,000 respectively, the average will be calculated by results from Week 2 Day 8 and Week 5.

The primary efficacy endpoint will be summarized as overall platelet response rate (ORR) with exact unconditional 95% confidence intervals (CI) by treatment group. The ORR difference and exact unconditional 95% CI will be provided between each of active treatment groups and placebo group, and between two active treatment groups. The p-value from Fisher's exact test will be presented.

For patients whose ORR cannot be adequately determined, their ORR will be imputed using a non-responder imputation (NRI) approach.

Summary statistics will be provided on the number (%) of patients achieving platelet response by each treatment and the combined active treatment groups. The differences in the ORR, 95% CI and p-value from a Fisher's exact test will therefore be provided for:

- Each active treatment group (200 mg BID, 400 mg BID) vs. placebo
- Combine active treatment groups vs. placebo
- 200 mg BID vs. 400 mg BID.

A logistic regression model will also be performed on platelet response as dependent variable and treatment group, baseline platelet count and prior TPO-receptor agonist use as covariates. The odds ratio for the treatment effect compared to placebo (together with 95% CI and p-value) will be provided.

Bar plots on difference in proportions of ORR and exact unconditional 95% CI will be provided by treatment group and combined active treatment group.

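### The stated 82.7% power follows its disclosed normal approximation but understates the planned Fisher's exact test, whose exact power at the same inputs is 93.9% (92.2% if the one-sided p is doubled)

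*Protocol*

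**What the plan says.** Protocol 7.4 states that 24 patients in an active group against 12 on placebo "will provide approximately 82.7% power to detect a difference between response rates of 50% and 1" per cent, "at the 2-sided 5% significance level". The synopsis has the same figure. SAP 4.4 gives it to one more decimal: the sample size "will provide approximately 82.74% power to detect a difference" between the same two rates.

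The method is disclosed in all three places. Protocol 7.4 describes it as the "2-sided Fisher's Exact test using the normal approximation method", run in PASS 15.

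The analysis itself is the exact test. Under Protocol 7.7.3 the primary endpoint is "analyzed using Fisher's exact test to compare the difference in ORR between each active treatment group and placebo". SAP 8.1.1 confirms it: "The p-value from Fisher's exact test will be presented". Protocol 7.7 sets the level: "All statistical tests will be 2-sided using a 5% significance levels", applied to each pairwise comparison with placebo without multiplicity adjustment. Both documents fix SAS 9.4 or later as the software. Neither says how the two-sided Fisher p-value is formed.

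**The concern.** The only power figure in the plan comes from a large-sample approximation, while the test to be run is exact. A normal approximation to a difference in proportions is doubtful when one arm has 12 patients and an assumed response rate of 1%, because the expected count in that cell is 0.12. A reader takes the figure as the power of the planned test. If the two differ materially, the plan misreports the operating characteristic that justifies its size. The direction also matters: an overstatement would mean too few patients, whereas an understatement leaves the design intact and calls only for a corrected text.

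**Working it through.** **Inputs.** From Protocol 7.4 and SAP 4.4: n₁ = 24 (one active group), n₂ = 12 (placebo), p₁ = 0.50, p₂ = 0.01, α = 0.05 two-sided. All figures are for one active group against placebo.

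**Step 1: reproduce the stated figure.** Use the normal approximation with pooled variance under the null, unpooled variance under the alternative, and a continuity correction.

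- Difference: d = 0.50 − 0.01 = 0.49
- Pooled rate: (24 × 0.50 + 12 × 0.01)/36 = 12.12/36 = 0.3367
- SE₀ = √[0.3367 × 0.6633 × (1/24 + 1/12)] = 0.1671
- SE₁ = √[0.50 × 0.50/24 + 0.01 × 0.99/12] = 0.1060
- Continuity correction: c = ½ (1/24 + 1/12) = 0.0625
- Power = Φ[(d − c − 1.96 SE₀)/SE₁] = Φ[(0.4275 − 0.3275)/0.1060] = Φ(0.943) = 0.8273

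This matches the protocol's 82.7% and lies within 0.01 point of the SAP's 82.74%. Without the continuity correction the same formula gives 0.937, so the correction accounts for almost all of the gap found below. The documents do not mention a continuity correction; it is inferred from the match.

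**Step 2: exact power of the planned test.** Enumerate all 25 × 13 = 325 possible outcomes (a active responders, b placebo responders). Mark those with two-sided Fisher p ≤ 0.05 and sum their probabilities under Binomial(24, 0.50) × Binomial(12, 0.01). Two conventions for the two-sided p are in play:

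- A: sum the probabilities of all tables no more probable than the observed one.
- B: double the one-sided p.

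| Placebo responders b | P(b) | Smallest a that rejects, A | P(reject given b), A | Smallest a that rejects, B | P(reject given b), B |
|---|---|---|---|---|---|
| 0 | 0.8864 | 8 | 0.9680 | 8 | 0.9680 |
| 1 | 0.1074 | 11 | 0.7294 | 12 | 0.5806 |
| 2 | 0.0060 | 13 | 0.4194 | 14 | 0.2706 |

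(The thresholds are those in favour of active. Three or more placebo responders add less than 0.0001.)

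- A: 0.8581 + 0.0784 + 0.0025 = 0.939 (0.9389 unrounded)
- B: 0.8581 + 0.0624 + 0.0016 = 0.922 (0.9221 unrounded)

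The p-values at the boundaries are 0.033 (A) and 0.049 (B) for 8/24 vs 0/12. For 11/24 vs 1/12 they are 0.031 (A) and 0.052 (B), so the convention decides significance at that outcome.

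**Step 3: the gap.** 93.9 − 82.7 = 11.2 points under A; 92.2 − 82.7 = 9.5 points under B.

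**Side check on the placebo rate (reviewer's assumption, not in the documents).** Holding the active rate at 50% and raising the placebo rate, exact power reaches 80% at a placebo rate of about 5.5% (A) or 3.8% (B). At an assumed 5% it is 81.5% (A) or 74.9% (B).

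**The case against.** The strongest reply is that nothing here is wrong. The text says the figure is approximate, names the normal approximation in the following sentence, and gives inputs and software; the figure then reproduces. It errs on the safe side. Section 3.1.2 refers to "the desired study power (typically 80% for a Phase 2 study"), and the design passes that mark by the stated method and by both exact conventions. No decision about the test, the level or the number of patients would change.

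Most of this stands. A reader might infer an arithmetic error; the reproduction rules that out. Disclosure, however, does not bring an approximation close to its target, and a gap of 9.5 to 11 points is large for a figure described as approximate.

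A reader might also infer from the side check that the trial is underpowered. The documents do not support that. They tie the power to 50% against 1% and give no alternative placebo rate. The side check varies only one arm, whereas the documents put the active rate at 50% or more. With an illustrative 60% active rate and convention A, exact power at a 5% placebo rate is 94.6%; with 40% active and 1% placebo it is 75.5%. The sensitivity therefore runs both ways and concerns the assumed rates. It is not a fault in the 82.7%.

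**Conclusion.** The point holds as a minor, conservative misstatement. At the documents' own inputs the planned two-sided Fisher's exact test has power 93.9% (convention A) or 92.2% (convention B), so the stated 82.7%/82.74% is too low by about 11 or 9.5 points. The result rests on 24 against 12 evaluable patients, true rates of 50% and 1%, and rejection at p ≤ 0.05. The sample size is adequate under those inputs.

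Nor should 93.9% be read as assured, or as grounds for fewer patients. It depends on the 1% placebo rate, for which Protocol 7.4 cites no source; the pilot study cited there is given in support of the active rate only.

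**What to change.** In Protocol 7.4, the synopsis and SAP 4.4:

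1. State the exact power of the two-sided Fisher's exact test at 50% against 1%, and name the convention: 93.9% if the p-value sums the tables no more probable than the observed one, or 92.2% if the one-sided p is doubled.
2. Keep 82.7%/82.74% only as the record of the normal approximation used to choose the sample size.

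Optionally, add one sentence that the figure depends on the 1% placebo rate: with active held at 50%, exact power falls below 80% above a placebo rate of about 5.5% (3.8% with doubling), labelled as a sensitivity assumption. If a fuller display is wanted, vary the active rate as well.

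The cost is a short text edit in three places. It needs no extra patients and no change to the test, the level or the sample size.

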7.5 Analysis Sets

The following analysis sets will be used in the statistical analyses.

Safety set: The safety set will consist of all subjects who receive at least 1 dose of study drug (SKI-O-703 or placebo). Subjects will be analyzed according to the treatment they received. This analysis set will be used in the analysis of demographic and safety data.

Intent-to-Treat (ITT) set: The ITT set will consist of all randomized subjects who receive at least 1 dose of study drug (SKI-O-703 or placebo) and have at least 1 post-baseline platelet assessments. Subjects will be analyzed according to the treatment arm to which they were randomized. This analysis set will be used for efficacy summaries, including the analysis of the primary endpoint.

Per-protocol (PP) set: The PP set will consist of all subjects in ITT set with no major protocol violations. Major protocol violations will be identified during the study. Subjects will be analyzed according to the treatment arm to which they were randomized. This analysis set will be used for efficacy summaries, including the analysis of the primary endpoint.

Pharmacokinetic (PK) set: The PK set will consist of all subjects who receive SKI-O-703 and have at least 1 measurable plasma concentration. Subjects who have partial data and/or major protocol deviations that may impact PK, and subjects who experience emesis, will be evaluated on a case-by-case basis and may be excluded from the PK analysis set. This analysis set will be used for summaries of PK data.

Pharmacodynamic (PD) set: The PD set will consist of all subjects who receive at least 1 dose of study drug (SKI-O-703 or placebo) and have at least 1 evaluable postdose PD value. Subjects who have partial data and/or major protocol deviations that may impact PD will be evaluated on a case-by-case basis and may be excluded from the PD analysis set. This analysis set will be used for summaries of PD data.

Pharmacokinetic (PK)/pharmacodynamic (PD) set: All subjects included in the PK and PD analysis sets. This analysis set will be used for the PK/PD analyses.

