1.3 Dose Rationale

SKI-O-703 was safe and well-tolerated in healthy volunteers when administered as single ascending doses over the dose range of 50 to 800 mg (Study OSCO-P1201), and multiple ascending doses at 200 mg QD, 400 mg QD and 200 mg BID for 7 days (Study OSCO-P1202). Based on the safety data from the various doses administered in these studies, there are no specific considerations that would concern the use of SKI-O-703 at doses proposed in this Phase 2 study.

Following multiple ascending doses of SKI-O-703 at 200 mg QD, 400 mg QD, and 200 mg BID (Study OSCO-P1202), a reduction in the PD endpoint “percentage of basophils expressing CD63+” was observed in healthy volunteers; on average, CD63+ expressing basophils were suppressed by 95%, 99% and 86% at steady state (Day 7) following administration at 200 mg QD, 400 mg QD, and 200 mg BID, respectively. Thereafter, the suppression of basophils expressing CD63+ was maintained at -72% or below for up to 2 and 8 hours following once-daily dosing at 200 mg and 400 mg, respectively, and up to 12 hours (ie, over a full 24-hr period) following twice-daily dosing at 200 mg. As the PD effect was sustained for longer after twice-daily dosing compared to once-daily dosing, twice-daily dosing at 200 mg and 400 mg has been selected.

As 400 mg BID has not been studied previously in humans, exposure (C_{max} and $AUC_{0-\tau}$) to SKI-O-592, M2, and M4 following 400 mg BID dosing has been estimated based on data observed previously at different dose levels. To ensure that predictions are cautious and

robust, steady-state C_{max} and $AUC_{0-\tau}$ following 400 mg BID have been predicted in 2 ways using data from Study OSCO-P1202:

1. AUC_{0-12} (400 mg, Day 1) \times Accumulation Ratio (200 mg BID)

2. PK Parameter (200 mg BID, Day 7) \times 2

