7.7.6.3 Exploratory PK/PD Analyses

PK/PD relationship between plasma concentrations of SKI-O-592, M2, and M4 and change from baseline in the percentage of activated CD63+ basophils in peripheral blood on Day 1 and Week 12 will be assessed. Individual and mean plasma concentrations of SKI-O-592, M2, and M4 will be plotted versus change from baseline in the percentage of activated CD63+ basophils in peripheral blood on Day 1 and Week 12.

Exploratory PK/PD modeling may also be performed; full details will be provided in a separate Statistical Analysis Plan.

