##### **4.6.4. Pharmacokinetic (PK) set**

The PK set will consist of all patients who receive SKI-O-703 and have at least 1 measurable plasma concentration. Patients who have partial data and/or major protocol deviations that may impact PK, and patients who experience emesis, will be evaluated on a case-by-case basis and may be excluded from the PK analysis set. This analysis set will be used for summaries of PK data.

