#### **4.6.6. Pharmacokinetic (PK)/pharmacodynamic (PD) set**

All patients included in the PK and PD analysis sets. This analysis set will be used for the PK/PD analyses.

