## **11. Pharmacodynamics**

### **11.1. Pharmacodynamic Data Handling**

Subjects with baseline CD63+ values below the limit of detection will be defined as low responders and excluded from the PD set and all summaries of PD data. Baseline will be defined as the percentage of activated CD63+ cells at predose samples on Day 1.

All PD data will be rounded to 3 significant figures for reporting purposes. The only exceptions will be actual sampling times and  $TE_{max}$  (which will be rounded to 2 decimal places). Summary statistics will be rounded to the same precision as individual data, with the exception of n (which will be reported as an integer).

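### As defined, the PK/PD set leaves out every placebo subject, so the exploratory concentration-effect analysis has no zero-exposure data after baseline

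*Protocol*

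**What the plan says.** Three definitions in Protocol 7.5 combine.

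- PK set: "The PK set will consist of all subjects who receive SKI-O-703 and have at least 1 measurable plasma concentration". SAP 4.6.4 carries the same restriction: "The PK set will consist of all patients who receive SKI-O-703 and have at least 1 measurable plasma concentration".
- PD set: open to anyone dosed with active drug or placebo who has an evaluable postdose PD value (Protocol 7.5, SAP 4.6.5).
- PK/PD set: "All subjects included in the PK and PD analysis sets. This analysis set will be used for the PK/PD analyses". SAP 4.6.6 matches: "All patients included in the PK and PD analysis sets. This analysis set will be used for the PK/PD analyses".

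The analysis that uses this set is in Protocol 7.7.6.3: "Individual and mean plasma concentrations of SKI-O-592, M2, and M4 will be plotted versus change from baseline in the percentage of activated CD63+ basophils", for Day 1 and Week 12. Modelling is optional there and is left to a separate SAP. The SAP under review lists the PK/PD objective (2.3) and defines the set, but describes no PK/PD analysis.

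Protocol 6.5.3 takes PD samples at 8 times on each of the two days from everyone in the PK/PD subset, without excepting placebo. SAP 11.1 sets the PD baseline at the Day 1 predose sample. It also rules that subjects whose baseline is below the limit of detection "will be defined as low responders and excluded from the PD set and all summaries of PD data".

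**The concern.** A concentration-effect analysis needs to know what the marker does over the same hours and weeks when no drug is present. Placebo subjects supply that, and Protocol 3.1.2 gives reduction of bias in the PK and PD evaluation among its reasons for a placebo-controlled design. The set definition removes them from the one analysis that relates effect to SKI-O-592, M2 and M4 concentrations.

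Three kinds of non-drug change could then be read as drug effect:

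- change within the day after the predose sample;
- regression to the mean, which dropping subjects with undetectable baselines may increase;
- drift over 12 weeks, when the Week 12 plot is read alone, since even its predose sample is taken on treatment.

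At stake is the first exploratory objective (Protocol 2.3).

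**Working it through.** The plan gives no figure on this point to reproduce. The check is set logic, a count, and an illustration with assumed inputs.

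**1. Who is in the set.** PK set = received SKI-O-703 and has a measurable concentration. PD set = received active drug or placebo and has a PD value. Subjects in both: active only, so the placebo count is 0. A union would admit placebo. It would also admit run-in subjects, who give PK samples but no PD samples, and subjects with a single Week 12 trough and no PD sample (Protocol Table 2, footnote g). That is implausible for a paired analysis.

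**2. What zero-exposure data remain.** Assume a subset of 20 that follows 2:2:1.

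- Placebo: 20 × 1/5 = 4. Active: 20 − 4 = 16.
- Zero-concentration pairs certain under the present definition: 16 × 1 = 16 (Day 1 predose), each with change 0 by definition.
- Placebo samples collected but not used: 4 × 8 × 2 = 64. Less 4 Day 1 predose samples, that leaves 60 after baseline.
- The 95% range for the placebo count is 1 to 8 (binomial, 20 draws at 0.2). It is 1 to 7 if 20 are drawn from the 60 − 5 = 55 subjects outside the run-in, 12 − 1 = 11 of them on placebo. The chance of no placebo subject is 0.8^20 = 1.2%, or 0.3% by the second method.

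**3. Illustration.** Model: change = E0 + Emax × C/(EC50 + C), where E0 is the non-drug change.

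Inputs from Protocol 1.3: the predicted 400 mg BID AUC of 14600 and Cmax of 6160 are twice the 200 mg BID values, so 200 mg BID has 14600/2 = 7300 and 6160/2 = 3080. The fed-state Cmax is 56% lower, hence 3080 × 0.44. Suppression of 72% at the 200 mg trough is taken from the healthy-volunteer result, held "up to 12 hours (ie, over a full 24-hr period) following twice-daily dosing at 200 mg".

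Assumed inputs: 8/8/4 subjects, total plateau effect of −95, between-subject and residual SDs of 10 points, and E0 of 0, −20 or −40. The true maximum drug effect is −95 − E0, so −75 when E0 = −20 and −55 when E0 = −40.

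| Fit | E0 = −20 (true −75) | E0 = −40 (true −55) |
|---|---|---|
| Active only, Week 12, E0 fixed at 0 | −95 | −94 |
| Active only, Day 1 and Week 12, free Week 12 offset, pure 12-week drift | −75, SD about 3 | −55, SD about 3 |

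Other results:

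- Active only, Week 12, E0 free: SD of the maximum drug effect about 60 to 100 points, depending on fitting bounds and assumed exposure profile.
- Week 12 with 4 placebo subjects at concentration 0: bias removed, SD about 6.
- E0 = 0: no bias in the active-only fit.
- Joint two-day active-only fit with a Day 1 postdose non-drug shift also left free: SD 46 to 81.

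Active-only data can therefore recover a pure 12-week shift if both days share Emax and EC50. They cannot usefully separate drug effect from non-drug change already present after dosing on Day 1.

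**The case against.** The strongest reply is that little is lost. Protocol 7.7.6.2 and SAP 11.2 summarise CD63+ change by treatment, day and nominal time, and the PD set includes placebo. Drift will therefore be visible at the same sampling times. The committed PK/PD work is graphical. Modelling is optional, belongs to a separate SAP that is not available here, and no document plans an active-only fit with E0 fixed at 0. The two dose levels and the spread of concentrations within subjects also carry some model-dependent information. All of this stands, and it limits the point to one exploratory analysis.

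A reader might also argue that the wording permits a union, or that placebo samples would enter as zeros: Protocol 6.5.1 takes PK samples from the whole subset, and SAP 10.1 sets values below quantification to zero. The documents do not say whether placebo samples are assayed. The PK set's condition of receiving SKI-O-703 excludes those subjects in any case. If the sponsor intended a union, both documents need to say so.

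Three stronger inferences are tempting, and the documents do not support them.

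- That the analysis has no zero-concentration data at all. Each active subject in the subset has a Day 1 predose sample; it simply carries no information on non-drug change.
- That the trial cannot separate drug effect from non-drug change. The by-treatment summaries on the PD set allow that comparison.
- That Week 12 active data would cover only about the top quarter of the effect range. This carries healthy-volunteer averages at Day 7 over to patients at Week 12.

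**Conclusion.** The point holds in a limited form. On the natural reading, no placebo subject enters the PK/PD set. The plots in Protocol 7.7.6.3, and any model restricted to this set, then have no zero-exposure data after baseline. Within-day change, regression to the mean and, when Week 12 is viewed alone, 12-week drift would appear there as concentration effects.

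The size of any bias is unknown. The non-drug changes of −20 and −40 points are assumptions chosen for illustration; with none there is no bias. It would be wrong to conclude that the objective cannot be answered without bias. The figure of about 4 placebo subjects assumes that a subset of 20 follows 2:2:1, and the low-baseline exclusion in SAP 11.1 could lower it. No primary, secondary or safety conclusion depends on this analysis. It is a minor point, worth acting on because the control data are already collected.

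**What to change.** In Protocol 7.5 and SAP 4.6.6, define the PK/PD set as PD-set subjects with at least one paired concentration and PD value, plus placebo subjects in the PD set with concentration set to 0. In Protocol 7.7.6.3, show placebo as the zero-exposure reference in the Day 1 and Week 12 plots. In the separate PK/PD SAP, require any model to estimate the zero-concentration effect from these data.

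The cost is wording in two documents and a little extra analysis. No new subjects, visits or samples are needed.
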